# 5.2 KEY DEFINITIONS

### 5.2.1 Study Day

Study Day 0 is the randomisation day. Subsequent days are numbered consecutively (Day 1, Day 2, etc.). Before Day 0, study days are numbered sequentially with negative values (i.e., Day -1, Day -2, etc.). This notation is used because the first dose of study medication is taken the day after the randomisation visit in Treatment Period A (and the day after Visit 5 in period B).

### **5.2.2** Baseline Values

Baseline values will be defined separately for each treatment period, unless stated otherwise.

For the primary efficacy endpoint (mean change from baseline to Week 4 in weekly average of the daily IPF Coughing Severity Scale score), period-specific baseline will be used in the analysis, which is the average of the 7 calendar days up to and including the date of Visit 2 for Treatment Period A and the average of 7 calendar days up to and including the date Visit 5 for Treatment Period B.

For secondary efficacy endpoints related to change from baseline, the period-specific baseline will be used when available; for those endpoints for which a period-specific baseline is not available

(cough frequency and Hull Airway Reflux Questionnaire), the baseline in Treatment Period A will be used.

For safety assessments, baseline will be Visit 2 for Treatment Period A and for Treatment Period B it will be Visit 5.

For both safety and efficacy assessments, if the period-specific baseline is missing for Treatment Period A the value from Visit 1 will be used. If this is missing change from baseline will not be calculated. If the period-specific baseline is missing for Treatment Period B the value from Visit 2 (first preference) or visit 1 (second preference) will be used. If both are missing change from baseline will not be calculated.

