10.1.6 Ambulatory Cough Monitor

Subjects will be fitted with an ACM (the Leicester Cough Monitor¹⁰ [LCM]) to record cough frequency over 24 hours at Visits 2, 4 and 7.

The LCM will be started prior to the subject leaving the clinic to monitor cough frequency over 24 hours. After this period, the subjects will either return the monitor to the clinic or collection from the subjects will be organised. Cough frequency will be determined by a central evaluation service

Protocol No.: ORV-PF-01 Final V4.0 (US) Page 46 of 85

¹⁰ Intellectual property rights to the Leicester Cough Monitor owned by [name] and King's College Hospital NHS Foundation Trust

Product: ORVEPITANT Protocol No.: ORV-PF-01 NeRRe Therapeutics Ltd

(Department of Respiratory Medicine, Kings College Hospital, London, UK [Kings]) using standardised methodology and with appropriate quality control processes.

On the three occasions that cough frequency is assessed, patients will be provided with a paper form on which they will record the times during the recording period that they were asleep.

Analysed data will be transferred to for statistical analysis. Kings will be provided with subject identifier information but will not have access to the randomisation code.

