### 7.1 PRIMARY AND SECONDARY EFFICACY ANALYSIS

Efficacy endpoints will be summarised separately for each cohort by descriptive statistics or counts and percentages for each treatment group at each time point, as appropriate. All statistical hypothesis tests and confidence intervals will be two sided, using a type I error rate of 0.05. No adjustments for multiple comparisons will be used.

The change from baseline of parameters in Week 4 (and Week 2 where also relevant) will be summarised for each treatment group in the FAS population.

Statistical comparisons for the primary and secondary endpoints will be done separately for each cohort as described below in each subsection. For the primary endpoint and secondary endpoints that are a daily numerical or verbal rating scale, an analysis of covariance (ANCOVA) model will be used with the response variable as the change from baseline in the mean score at the timepoint of interest, and predictor variables (fixed effects) as treatment, baseline mean score for the endpoint, period and interaction effect between treatment and period. Subject will be included as a random effect. Investigation of other covariates such as age and sex and their impact on the results may be done post-hoc. Sample SAS code for the ANCOVA is provided below.

Normality of error terms may be checked with QQ plots or other methods. If normality assumptions are considered severely violated, log transformation will be attempted first to see if that fixes the issue. If the normality assumption is still violated after applying transformation, a non-parametric method (e.g., Wilcoxon signed-rank test) will be used for conducting treatment comparison between orvepitant (10 mg or 30 mg once daily) and placebo.

All efficacy data, both patient-reported scores/assessments and derived parameters, will be listed.

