### 7.1.2.10 Cough Frequency

Cough frequency is measured using the Leicester Cough Monitor ambulatory cough monitor applied for 24-hours at the Baseline visit (Period A) and in Week 4 of each treatment period.

Cough frequency data will be log transformed before modelling (descriptive summaries will still be performed using the original values). If there are subjects with cough frequencies of 0, 1 will be added prior to log transformation and will then be subtracted from the back-transformed value. Data will be tested for normality prior to transformation. An ANCOVA model similar to the primary endpoint will be used except only baseline for Period A will be used as there is no baseline available for Period B. The following will be assessed for Mean change from baseline to Week 4:

Page 31 of 50

Statistical Analysis Plan Final V1.0, 14 Mar 2024

NeRRe Therapeutics Ltd Protocol: ORV-PF-01

- Average number of coughs per hour in the 24 hour period
- Average number of coughs per hour in the awake period
- Average number of coughs per hour in the asleep period
- Average number of bouts per hour in the 24 hour period
- Average number of bouts per hour in the awake period
- Average number of bouts per hour in the asleep period
- Average number of coughs in a cough bout in the 24 hour period
- Average number of coughs in a cough bout in the awake period
- Average number of coughs in a cough bout in the asleep period.

The treatment effect will be estimated using the ratio of geometric means (i.e. the difference between the treatments least squares means [adjusted means] on the log scale, back-transformed to the original scale). The ratio of GM ratios is the geometric mean ratio (orvepitant [10 mg or 30 mg once daily]/ Placebo) of the Week 4/baseline result. The adjusted geometric mean (GM) ratio (Week 4/baseline) and corresponding 95% CIs for each treatment group, ratio of GM ratios (orvepitant [10 mg or 30 mg once daily]/Placebo), 95% CIs for the ratio of GM ratios and the p-value from the hypothesis test of no difference between the treatment groups at Week 4 will be presented by cohort.

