### 7.1.2.14 Hull Airway Reflux Questionnaire

The Hull Airway Reflux Questionnaire is a 14-item questionnaire that assesses airway hypersensitivity, particularly that associated with reflux of gastric contents. Total score is calculated as sum of individual items. The questionnaire will be completed by subjects at Visits 2, 4 and 7.

Mean change from baseline to week 4 for the total score will be analysed with an ANCOVA model similar to that used for the primary endpoint separately by cohort except only baseline for Period A will be used as there is no baseline available for Period B.

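### A failed Visit 2 cough-monitor recording removes complete treatment pairs from the cough-frequency analysis, although that baseline cancels from their orvepitant/placebo contrast

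*SAP*

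**What the plan says.** Protocol 10.1.6 has the monitor fitted "to record cough frequency over 24 hours at Visits 2, 4 and 7". The schedules of events in both documents show no recording at Visit 1 or Visit 5.

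SAP 5.2.2 (and, in the same terms, Protocol 11.1.1) uses period-specific baselines where they exist. For the two measures without one, the rule reads: "cough frequency and Hull Airway Reflux Questionnaire), the baseline in Treatment Period A will be used". A missing Period A baseline is replaced by the Visit 1 value, and then: "If this is missing change from baseline will not be calculated". A missing Period B baseline is replaced by Visit 2, then by Visit 1, and then: "If both are missing change from baseline will not be calculated".

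The model in SAP 7.1 takes change from baseline as the response, with fixed effects "treatment, baseline mean score for the endpoint, period and interaction effect between treatment and period". It adds: "Subject will be included as a random effect". SAP 7.1.2.10 applies this to log cough frequency, "except only baseline for Period A will be used as there is no baseline available for Period B", and lists nine monitor-derived measures. It also asks for adjusted Week 4/baseline geometric mean ratios for each treatment and for the ratio between treatments. SAP 5.3.1 sets no imputation as the default.

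HARQ follows the same pattern. SAP 7.1.2.14 says: "The questionnaire will be completed by subjects at Visits 2, 4 and 7".

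**The concern.** The two fallback rules lead nowhere for cough frequency. Period A would need a Visit 1 recording. Period B would need Visit 2, which is the value that failed, or Visit 1. One failed recording therefore leaves both change scores undefined and the baseline covariate missing, and the subject drops out. The likelihood methods in Protocol 11.11 deal with missing outcomes. They do not help when the response is undefined because its baseline is absent.

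A subject with valid Week 4 recordings on both treatments carries all the information that a crossover needs for the orvepitant/placebo comparison. Discarding that subject costs precision on the trial's only objective cough measure, in cohorts planned at 37 evaluable subjects each.

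The recording is exposed to failure. Protocol 8.7.2 starts it as the subject leaves the clinic, with randomisation on the same day and dosing from the following evening, and no repeat is scheduled. The safeguards in SAP 5.3.1 cover the eDiary and the clinic questionnaires and do not mention the monitor.

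**Working it through.** **1. The plan's own figure.** Inputs from SAP 2.5.1: SD of the paired difference 2.7, difference 1.5, two-sided 0.05, 90% power. The noncentrality at n = 37 is 1.5 × √37 / 2.7 = 3.38. The noncentral t gives power 0.908 at n = 37 and 0.8998 at n = 36, so 37 is reproduced. It is a primary-endpoint figure; no sample size or SD is given for cough frequency, and 37 serves here only as a scale.

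**2. Cancellation.** Let b be a subject's single log baseline and Y the log Week 4 value:

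(Y_orv − b) − (Y_pbo − b) = Y_orv − Y_pbo

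Adding 1 before taking logs does not alter this. With both periods observed, the treatment effect averaged over periods is the mean of the two sequence-specific within-subject differences, and a covariate that is constant within subject does not enter it.

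**3. Numerical check.** A 2×2 crossover of 37 subjects was simulated with one shared baseline per subject (assumed log-scale SDs: between-subject 0.9, within-subject 0.5). The mixed model of SAP 7.1 was fitted by REML in four forms: change or raw Week 4 value, each with and without the baseline covariate.

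| Sequence sizes | All four forms, complete pairs | SAP rule, 4 baselines missing |
|---|---|---|
| 18/19 | −0.11824, SE 0.10488 | −0.13706, SE 0.11319 |
| 15/22 | −0.14232, SE 0.10801 | −0.16885, SE 0.11585 |

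In the last column every Week 4 pair was complete. The shift in the estimate is what losing four random subjects does; it is not bias.

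**4. Size of the loss.** With complete pairs the SE scales as √(37/m), where m is the number of pairs left. The failure rates are assumptions.

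| Assumed failures | Pairs left | SE factor |
|---|---|---|
| 5% | 35 | √(37/35) = 1.028 |
| 10% | 33 | √(37/33) = 1.059 |
| 15% | 31 | √(37/31) = 1.092 |
| 20% | 30 | √(37/30) = 1.111 |

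**5. Subjects with one period.** Protocol 7.1 plans about 88 subjects, against 2 × 37 = 74 evaluable, a margin of 14, or 7 per cohort. A subject with one period contributes between-subject information, and baseline matters there. With 4 of 37 simulated subjects lacking Period B (sequences 18/19), the SAP model gave −0.127 (SE 0.11406) and the raw model without baseline −0.110 (SE 0.11599), an SE ratio of 0.11599/0.11406 = 1.017. Cancellation is therefore exact only for complete pairs.

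**6. Two remedies compared.** The setting is 44 subjects per cohort, 7 of them with one period (an assumption taken from the margin in step 5).

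- Dropping baseline for everyone: over a range of assumed correlations, the SE was 0.5% to 2.3% larger than under the SAP model with no failed recordings, about equal with one failure, and smaller by 0.4% to 2.2% with two and 3.1% to 5.0% with four.
- Keeping baseline where available, with a missing-baseline indicator: never worse than the SAP model in simulation, and an SE about 1% to 6% smaller with two to four failures.

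**The case against.** Four arguments can be made for the plan as it stands.

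- **Baseline does some work.** It sharpens the contribution of subjects with one period, and it supports the missing-at-random assumption in Protocol 11.11. Step 5 confirms the first part. A reader might infer from the cancellation that baseline is useless here and should be dropped from the model. The documents do not support that: subject is a random effect, data up to withdrawal are kept, and incomplete subjects are planned for. This argument stands, and it decides the form of the fix.
- **The endpoint is defined as change, and adjusted Week 4/baseline ratios are specified.** This stands for the ratios, which need a baseline. It does not count against modelling the Week 4 value for the contrast. With baseline as a covariate, the change and Week 4 models are the same model with the baseline slope shifted by one, and they give the same treatment contrast.
- **HARQ is unlikely to be affected.** A reader might infer an equal risk, because the visit pattern is the same. SAP 5.3.1 describes staff supervision, forced completion of each questionnaire before the next, and spare devices, so a missing Visit 2 HARQ should be rare. This stands.
- **The size is hypothetical and the endpoint secondary.** This also stands. No document gives a failure rate or a cough-frequency variance, and Protocol 8.7.2 delays dosing so that the baseline recording can finish.

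None of these gives a reason to discard a subject with two valid Week 4 recordings.

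**Conclusion.** The point holds for ambulatory cough frequency. As written, a failed Visit 2 recording excludes a complete treatment pair whose orvepitant/placebo contrast does not depend on the missing value.

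The cost is precision only. It is about 3% to 6% on the width of the confidence interval if 2 to 4 of 37 pairs are lost, and somewhat less when subjects with one period are also analysed. This rests on an assumed failure rate and on borrowing the primary endpoint's 37.

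A reader might conclude that the planned treatment estimate is wrong or biased. Nothing in the documents shows that: the baseline is taken before dosing, and the rule loses information without favouring either treatment. The primary endpoint has its own diary baseline in each period and is untouched. This is a cheap improvement to a secondary analysis.

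**What to change.** In SAP 7.1.2.10, with a cross-reference from 5.2.2, before unblinding:

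- For the treatment contrast, model the log Week 4 value with treatment, period, treatment by period and subject as a random effect.
- Keep the Visit 2 log baseline as a covariate where it exists. Where it is missing, set it to a constant, for example the overall mean, and add a missing-baseline indicator. Every subject with a valid Week 4 recording then stays in.
- Report the adjusted Week 4/baseline geometric mean ratios per treatment as planned, in subjects with a baseline, and footnote the two denominators.
- Apply the same rule to HARQ in 7.1.2.14 for consistency, expecting little gain.

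The cost is one extra model term, a few lines of text, and per-treatment ratios that may rest on slightly fewer subjects than the contrast. If no recording fails, the indicator drops out and the contrast equals the one now planned.

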### 5.3 DATA HANDLING CONVENTIONS

### 5.3.1 Missing Data

The primary and several secondary efficacy endpoints are derived from data recorded by the study participants in the eDiary each day. To minimise missed completion, and so missing data, the compliance with eDiary completion is monitored by the sponsor daily. If a participant has missed entries, and in particular during the critical periods before study visits 2, 4, 5 and 7, the site staff are contacted and they in turn contact the patient to enquire about potential problems and remind them to complete the diary each day.

The secondary efficacy endpoint questionnaires that are completed periodically at the clinic visits are done under the direct supervision of the site staff. Each questionnaire has to be answered in its entirety before the next one becomes available on the iPad on which they are completed. The sites also have spare iPads in case of technical problems.

Collectively, these processes result in a high degree of compliance and hence minimal missing data for each of the PRO endpoints.

For the participants who are discontinued or withdraw from the trial, all data until the point of discontinuation and/or withdrawal from the study will be used in the summary and analyses. In general, missing values will not be imputed for the analysis, unless otherwise specified.

See Section 6.4 for imputation of partial dates for prior and concomitant medications.

See Section 8.1 for imputation of partial dates for adverse events.

See Section 7.1.1 for handling rules of missing data when deriving weekly average of NRS score.

### **5.3.2** Visit Windowing

For summaries of by visit safety data, the CRF visit will be used. Unscheduled visits will be listed but not mapped to a specific analysis visit.

For summaries and analyses of efficacy data, the following table outlines the analysis visits that efficacy data will be mapped to. Efficacy assessments will be mapped to a study analysis visit as long as the study day(s) falls within the windows specified in Column A (Protocol allowed window for the visit) or Column B (Reasonable limits for out of window days for actual visit to be associated with nominal Visit). Efficacy data collected on days falling out of analysis visit windows (Column C) will be reviewed at the BDRM and may be assigned to an analysis visit window if appropriate.

Study Analysis Visit	Target Day for CRF Visit	A. Protocol allowed window for the visit (inclusive)	B. Reasonable limits for out of window days for actual Visit to be associated with nominal Visit	C. Unaccounted for days
Baseline (Visit 2)	0	N/A	N/A	N/A
Treatment Period A - Week 2 (Visit 3)	14	11 to 17	7ª to 10 18 - 20	1 to 6
Treatment Period A - Week 4 (Visit 4)	28	25 to 31	21 to 24 32 to 34 b	35 to 39
[Wash-out start]	29	N/A	N/A	N/A
End of Wash- Out / Start of Period B (Visit 5)	B0° [49]	N/A [46 to 52]	N/A [42 to 55]	N/A
Treatment Period B - Week 2 (Visit 6)	B14 [63]	B11 to B17 [60 to 66]	B7 a to B10 [56 to 59] B18 to B20 [67 to 69]	B1 to B6
Treatment Period B - Week 4 (Visit 7)	B28 [77]	B25 to B31 [74 to 80]	B21 to B24 [70 to 73] B32 to B34 b [81 to 83]	B35 to B39

a. Earliest day on which a 7 day data collection period is possible

The weekly average score is derived using scores recorded in the eDiary from the last 7 calendar days up to and including the date of the relevant visit (as defined in the visit window above).

Page 24 of 50

b. Last day a fully compliant subject will be able to dose (subjects are provided with 34 days of study medication)

c. Please note that for the purposes of visit window assignment only the clock is re-set for treatment period B

[] = nominal study day, where Baseline Visit 2 = Day 0; BDRM = blinded data review meeting

At least 4 scores are required to derive a weekly average. These four scores do not have to be on consecutive days. If 4 scores are not recorded in the eDiary the weekly average will be considered missing for that visit.

### 5.3.3 Data Dates

For diary data in particular, it is possible that the end date of the task can fall onto the day after the start date of the task (for example, if the diary completion is started just before midnight). In such instances, the start date will be used as the assessment date.

If the patient-reported date of first dose in each treatment period is missing, it will be assumed that the first dose is taken the day after the date of dispensing the drug (i.e., the day after the date of Visit 2 for Treatment Period A and the day after the date of Visit 5 for Treatment Period B).

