### 2.6.3 Planned and Actual Treatment

Planned treatment will be the one assigned per the randomisation list.

Actual (received) treatment might be different if the study medication kit(s) actually dispensed does not correspond to the kit(s) allocated by IWRS. Thus, actual treatment groups will be used for patients belonging to the Safety Analysis Set – according to the actual treatment dispensed to the patient. If the information on the kit number is not available at the time of the analysis, the actual treatment will be considered as equal to the planned one.

For the analysis of efficacy in the Full Analysis Set (FAS, study populations are defined in Section 4) the intent to treat principle will be followed and subject data will be assigned to the planned treatment group, regardless of the actual treatment provided.

Any occurrence of incorrectly administered treatment should be recorded as a protocol deviation.

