### 4 ANALYSIS POPULATIONS

# 4.1 SAFETY SET (SS)

All subjects who receive at least one dose of double-blind study drug irrespective of treatment received. Subjects will be analysed according to treatment received.

Statistical Analysis Plan Final V1.0, 14 Mar 2024

NeRRe Therapeutics Ltd Protocol: ORV-PF-01

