### 8.1 ADVERSE EVENTS

Adverse events will be coded using the latest available version of MedDRA (v26.0 or higher). All treatment-emergent AEs (TEAEs) from the start of study drug dosing will be collected. A TEAE is any AE that first occurred or worsened in severity following first dose. AEs that start during the wash-out period will be assigned to the treatment received during Treatment Period A for TEAE reporting; AEs that start following first dose in Treatment Period B up to end of follow-up will be assigned to the treatment received during Treatment Period B for TEAE reporting.

The following AE summaries will be presented:

- An overall summary table, including the number of events and number and percentage of subjects with:
  - o TEAEs
  - Subjects with at least one TEAE
  - Study drug-related TEAEs

Page 34 of 50

- Serious TEAEs
- o TEAEs with an outcome of death
- o Treatment-emergent AESIs
- Severe TEAEs
- o TEAEs leading to study drug discontinuation
- TEAEs by SOC and PT. This table will have a section for overall, and two subgroup sections for concomitant use of disease modifying therapies (yes, no [nintedanib or pirfenidone])
- Serious TEAEs by SOC and PT
- Treatment-emergent AESIs by SOC and PT
- TEAEs leading to study drug discontinuation by SOC and PT
- Related TEAEs by SOC and PT
- Maximum severity of TEAEs by SOC and PT

Non-treatment emergent AEs and TEAEs will be listed.

In addition, the following subject listings will be provided as tables:

- Deaths
- Serious TEAEs
- AESIs
- TEAEs leading to study drug discontinuation

For all AE tables summarised by SOC and PT, a subject contributes only once to the count for a given AE on the SOC level and on the PT level within SOC. SOC and PT levels will be sorted in descending order of frequency (subject count), followed by descending order of frequency (event count), followed by alphabetical order.

AEs will be classified as either related or unrelated to study medication. AEs with missing relationship to study drug are counted as related in the summary tables.

In the summary by severity, subjects reporting AEs at different severities will be counted only once at the highest severity reported within an AE level (SOC or PT). Severity categories will comprise of mild, moderate and severe.

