## 8.7 TREATMENT COMPLIANCE AND EXPOSURE

Definitions of exposure variables are provided in Table 2.

Table 2: Exposure variables definitions

Variables	Definitions
Duration of dosing (days)	Last dose of treatment – first dose of randomised treatment +1  The first and last days of treatment in each treatment period is used to derive the duration of dosing for each treatment (placebo and orvepitant).
Study treatment compliance (%)	100 * (total number of doses taken) / (total number of doses planned to be taken)  Total number of doses taken is calculated using the eCRF pages 'Drug Accountability" and "Drug Dispensing", based
	on the following:  Each bottle contains 34 tablets which is sufficient for the full 28 day dosing period plus overage. Number of doses taken = number of tablets dispensed (at Visit 2 [Period A] or Visit 5 [Period B]) – number of tablets remaining in the bottle (at Visit 4 [Period A] or Visit 7 [Period B]).
	The total number of doses planned to be taken is the number of days between the first visit in the period (Visit 2 or 5) and the Week 4 visit (Visit 4 or 7) for each period. If a subject is early discontinued prior to Week 4 within the period, 28 will be used for the total number of doses planned within the period.
Cumulative orvepitant exposure (mg)	In placebo period, Cumulative dose (in mg) = 0 In orvepitant 10 mg period, Cumulative dose (in mg) = number of doses taken * 10 In orvepitant 30 mg periods, Cumulative dose (in mg) = number of doses taken * 30

Note, if a subject interrupts treatment (for example due to an AE) but subsequently restarts treatment and completes, in total, the planned 4-week treatment period, an adjustment to the actual date range will be applied to the compliance calculation to include only those days that the subject was expected to take treatment (i.e., the dates during which treatment was interrupted will be excluded from the calculation).

Page 38 of 50

NeRRe Therapeutics Ltd Protocol: ORV-PF-01

The following information will be tabulated by treatment:

- Summary of drug duration
- Summary of cumulative orvepitant exposure (in mg)
- Summary of randomised study treatment compliance: Compliance will be summarised quantitatively and qualitatively for the category ( $\leq 50\%$ , >50 to  $\leq 80\%$ , >80 to <100%, =100%, >100 to  $\leq 120\%$ , >120%).

Listings of IMP dispense/administration and drug accountability data will be provided for the Safety Analysis Set.

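### SAP 5.3.3 fills in a first-dose date without evidence of dosing, so a subject who took drug in one period only can have adverse events counted under a treatment never taken

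*SAP*

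**What the plan says.** SAP 5.3.3 (Data Dates) opens its rule with "If the patient-reported date of first dose in each treatment period is missing" and continues that "it will be assumed that the first dose is taken the day after the date of dispensing the drug". The rule applies to each period separately: the day after Visit 2 for Period A, the day after Visit 5 for Period B. No exception is written for a period in which nothing was taken.

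Four other SAP sections bear on the result:

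- **4.1, Safety Set:** "All subjects who receive at least one dose of double-blind study drug irrespective of treatment received". This is a test on the subject. There is no separate test for each period.
- **8.1, Adverse Events:** "A TEAE is any AE that first occurred or worsened in severity following first dose". Events in the wash-out go to the Period A treatment. For the second period, "AEs that start following first dose in Treatment Period B up to end of follow-up will be assigned to the treatment received" in that period.
- **8.7, compliance and exposure:** "Number of doses taken = number of tablets dispensed" less the tablets left in the bottle. Each bottle holds 34.
- **6.4, concomitant medications:** allocation to Period A or Period B also turns on the date of first dosing in the period.

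Protocol 8.7.2 and 8.7.6 dispense the drug at the visit and have it started the following evening. Protocol 7.4 asks that subjects who permanently stop study drug be followed through the remaining visits.

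**The concern.** A first-dose date can be missing for two reasons: the subject dosed and did not record it, or the subject never dosed. SAP 5.3.3 treats both as dosed. The design leaves about a day between dispensing and the first tablet, so the second reason is possible in either period.

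Safety is a primary objective and is tabulated by treatment. In a crossover, an invented Period B start also marks the point at which events stop being counted under the Period A treatment. A subject who took orvepitant in Period A and never opened the Period B bottle would have later events shown under placebo. In the opposite sequence, events in a subject whose only treatment was placebo would be shown under orvepitant. The same subject would appear in the exposure table with no Period B exposure.

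**Working it through.** The plan states no figure on this point, so the check is a walk through the rules, followed by an illustration of scale.

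**Case 1: dosed in Period A, Period B bottle untouched.** Nominal days are from SAP 5.3.2, with Visit 5 at Day 49 and Visit 7 at Day 77.

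1. The subject is in the Safety Set (4.1) through Period A dosing.
2. The Period B first-dose date is missing. SAP 5.3.3 sets it to Day 49 + 1 = Day 50.
3. Under 8.1, events from the imputed first dose to the end of follow-up go to the Period B treatment. Visit 8 falls at Day 77 + 14 = Day 91, so the affected stretch is up to 91 - 50 + 1 = 42 days, or less if the subject leaves early.
4. Under 8.7, doses taken = 34 - 34 = 0. Compliance is 100 × 0/28 = 0%. Cumulative exposure is 0 mg whether the bottle held placebo, 10 mg or 30 mg tablets.

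Steps 3 and 4 disagree on whether the subject was treated in Period B, and no sentence in the SAP says which prevails.

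**Case 2: Period A bottle untouched, dosed in Period B.** The imputed first dose is Day 0 + 1 = Day 1. Events from Day 1 to Day 49 become treatment-emergent under the Period A treatment, although the subject had taken nothing by then.

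**Case 3: no dose in either period.** The subject fails the test in 4.1 and does not enter the safety tables.

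**Scale.** About 88 subjects in two equal cohorts (protocol 7.1) gives 88/2 = 44 per treatment column if everyone is dispensed both treatments. The number of undosed subjects, k, is not in the documents and is assumed here.

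- Share of a column: 1/44 = 2.3%; 2/44 = 4.5%.
- Denominator effect alone, with 10 subjects having an event: 10/42 = 23.8% against 10/44 = 22.7%, a shift of 1.1 percentage points.
- Denominator and events together, assuming a 30% event rate in dosed subjects. The lower value is 0.30 × (44 - k)/44 (no undosed subject has an event). The upper value is [0.30 × (44 - k) + k]/44 (all of them do):

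| k | Lower | Upper |
|---|---|---|
| 1 | 12.9/44 = 29.3% | 13.9/44 = 31.6% |
| 2 | 12.6/44 = 28.6% | 14.6/44 = 33.2% |
| 4 | 12.0/44 = 27.3% | 16.0/44 = 36.4% |

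**The case against.** The best defence is that 5.3.3 is a date convention and not an exposure rule. It does not say that an imputed date decides who was dosed, and both 4.1 and 8.1 speak of treatment received. If nothing was received in Period B, there is arguably no Period B treatment to which an event could be assigned. This fully answers Case 3. It does not settle Cases 1 and 2: the subject is already in the Safety Set, 5.3.3 states that a first dose is assumed to have been taken, and 8.1 allocates by first dose. A programmer following the text would have a date and would use it.

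SAP 2.6.3, which labels Safety Set subjects "according to the actual treatment dispensed to the patient", might be read as a second rule that equates dispensing with exposure. It is not one. It deals with kits that differ from the allocated kit, and it decides which drug label applies, not whether a dose was taken.

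The plan also has means of noticing such a subject: tablet counts (8.7), disposition with withdrawals by period (6.1), the discontinuation record (protocol 7.4) and the blinded data review meeting (4.3). These stand as ways to see the case before unblinding. None of them overrides the imputed date or moves the events. On denominators, SAP 12.2.5.2 says that the number exposed is usually the right base, so an inflated denominator is possible but not certain. That provision does not deal with where events are allocated.

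Finally, with a half-life of about 33 hours, a 21-day wash-out is 21 × 24/33 = 15.3 half-lives, so an event after Visit 5 is unlikely to reflect Period A drug. That is fair. But the SAP already assigns wash-out events to Period A as a convention, and an event should not be moved to a drug that was never taken.

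**Conclusion.** The concern holds for a subject dosed in one period who was dispensed the other period's drug and took none. For that subject the literal rule creates a dose that did not happen, can place events under an untaken treatment, and contradicts the zero doses derived in 8.7.

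The effect is minor. The documents do not give the number affected, and it is likely to be small; 1 or 2 of 44 is an assumption used only to show scale. No inferential safety tests are planned (SAP 8). The primary efficacy analysis uses planned treatment and diary averages tied to visit dates, so it does not depend on the imputed date.

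A reader might infer more than this, in two ways. The first is that anyone dispensed drug enters the Safety Set, or the Full Analysis Set, without dosing. Both definitions require a dose, and 5.3.3 does not redefine them. The second is that subjects who decline Period B are those who had trouble in Period A, which would give the error a known direction. Nothing in the documents supports that.

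**What to change.** Revise SAP 5.3.3 as follows:

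- **Evidence of dosing:** impute the first-dose date only when tablets dispensed minus tablets returned in that period is 1 or more.
- **All tablets returned:** treat the period as not dosed. Leave the date missing, keep the subject out of that treatment's safety column, and keep later events with the last treatment actually taken. If no dose has yet been taken, as in Case 2, events before the first real dose are not treatment-emergent. Apply the same status to the concomitant-medication split in 6.4.
- **Bottle not returned:** do not presume dosing. Classify the period at the blinded data review meeting from records already collected: the discontinuation record, and a plasma orvepitant sample where there is one. A concentration can reveal treatment, so someone outside the blinded team should read it and report only whether dosing is shown. A value below quantification cannot separate placebo taken from orvepitant not taken.

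SAP 2.6.3 needs no change.

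The cost is a few sentences in a revised SAP, which is currently Final V1.0 and would need signing again before unblinding. A revision may be due in any case: the SAP is based on protocol versions 3.0/3.1, the protocol is now V4.0, and SAP section 1 foresees updates after amendments. No new data are needed.
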